## **Abstract**

Nearly 30 million Americans have type 2 diabetes (T2DM), a disorder with serious health consequences such as cardiovascular and renal disease. Almost 90 million more have prediabetes, with estimates of 8 million undiagnosed (CDC, National Diabetes Statistics Report). Insulin resistance (IR) is a precursor to prediabetes and T2DM (NIDDK, Insulin resistance and prediabetes). There is evidence of IR in those with short sleep [normal weight (Matthews et al., 2012); obese (Liu, Kushida, & Reaven, 2013)]. The risk for developing diabetes in persons with difficulty in maintaining sleep is 1.84 times the risk of diabetes in those who do not have sleep issues which is very similar to the relative risk detected from another commonly recognized risk factor-- family history of diabetes (1.7-2.3) (Reutrakul & Van Cauter, 2014). For this pilot study we will recruit 20 young adults, accounting for attrition, age 18-25 years who have elevated HOMA-IR (based on established cut points), short sleep duration (< 7 hrs./night) and obesity (BMI  $\geq$  30) (another risk factor for IR), and use a two-group, pre-test/post-test experimental design including objective actigraphy data for sleep. The specific aims are to: 1) evaluate the feasibility and acceptability of a tailored intervention to extend sleep duration (SLEEP-Extend), 2) determine changes in sleep duration after SLEEP-Extend intervention, 3) evaluate IR levels before and after SLEEP-Extend, and 4) explore the potential mediators of diet and physical activity between sleep duration and IR. Screening data will include measures of sleep duration, age, IR and BMI. After enrollment, baseline data will include pre-test of sleep hygiene knowledge, self-report measures of diet and physical activity as well as one week of objective monitoring of sleep using actigraphy. After all baseline data are collected, participants will be randomly assigned to group. The SLEEP-Extend intervention group will receive sleep hygiene education and instructions to increase time in bed by one hour total each night for an additional 4 weeks. The attention control group will receive education on safety practices in an urban environment. Both groups will receive the sleep hygiene post-test immediately after the intervention, and they will continue with actigraphy monitoring for 4 weeks. After the 4-week intervention period, both groups will have measures of IR, BMI, final post-test of sleep hygiene knowledge, self-reported diet and physical activity, and an exit interview, and actigraphy data will be downloaded. This study will examine whether an intervention to extend sleep will result in behavior change to increase sleep duration and improve IR.

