
## **Study Methods**

**Design:** A two-group, pre-test/post-test experimental design will be used to examine the feasibility and estimate the effects of a sleep intervention (SLEEP-Extend) designed to extend sleep duration in obese, young adults with short sleep and IR. Participants will wear actigraphy watches for one week of baseline sleep data and for an additional four weeks during the intervention.

**Sample/Setting:** We will recruit from Emory Hospital and Emory affiliated hospitals (Children's Healthcare of Atlanta, Emory St. Joseph's, Emory Johns Creek, Emory Midtown) through nursing staff email listservs as well as through flyers on Emory University campus and in areas that might attract young adults, through course web announcements, listservs for student emails and through social media, 20 obese individuals age 18-25 years old with short sleep (duration less than 7hrs./night) and evidence of IR [HOMA-IR levels  $\geq 2.1$  using serum sample (Esteghamati et al., 2010)] (See Timeline). We want to ensure 10 participants are in both groups; therefore, based on our previous experience recruiting from this age group, we will recruit individuals to give us a final N=20 (10 in each group).

Inclusion criteria: 1) Age 18-25 years old, 2) Self-report short sleep, 3) BMI  $\geq 30$  (the World Health Organization's classification of being obese, 4) IR determined by serum analysis, 5) Be willing to extend time in bed (See intervention below) by one hour total per night, and 6) Read and speak English.

Exclusion criteria (all self-report): 1) Night shift workers (circadian disruption can alter glucose and insulin levels), 2) Diagnosed sleep disorder (e.g., sleep apnea, restless leg syndrome,) which may impact glucose, insulin, and other hormones, 3) Medical diagnosis of diabetes or pre-diabetes, 4) Pregnant or lactating women or history of gestational diabetes, 5) Actively or intentionally trying to lose or gain weight (alteration of glucose metabolism/insulin secretion), 6) Hospitalization in past 3 months for medical or psychiatric condition, or 7) Major chronic disease (e.g., cancer, Lupus). The 5-week study will be conducted during the middle of the semester when the longer holidays and final exams do not occur.

1. Data samples will not be saved/banked or archived for future use.

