### **PROCEDURES:**

For interested participants, initial screening on the telephone for age, average sleep duration, and BMI will be done and if eligible, an appointment will be set and instructions for fasting (participant will be instructed to not eat or drink anything for 8 hours) for the screening visit (Visit #1). At Visit #1 we will obtain written informed consent that will include information on screening process: eligibility of IR (from blood sample) and height and weight measures will be obtained for BMI. Blood samples will be analyzed within one week. If HOMA-IR level is elevated in these obese individuals with short sleep, then they will be contacted and 2 additional appointments will be made. If they do not have elevated HOMA-IR levels, the researcher will call and thank them for their interest and let them know they are not eligible. Visit #2, baseline (BL) visit, will be within 2 weeks of obtaining initial blood result and consent will be confirmed (for enrollment in the study) and other BL data will be collected. Also, participants will be given a sleep diary to complete and an actigraphy watch to wear for one week for BL sleep assessment. During visit #3 (intervention visit) which is one week after BL visit, the BL actigraphy data will be downloaded and the participant instructed to continue to wear the watch for 4 more weeks. Randomization to groups will occur, and each group will receive the appropriate intervention content for the group. Immediately after the intervention, the appropriate knowledge post-test will be given according to assigned group. The SLEEP-Extend group will decide on when they are able to extend their TIB. After 2 more weeks both groups will receive a telephone call to reinforce content and answer questions about extending TIB and sleep hygiene for SLEEP-Extend group and safety information in the control group. At this telephone call the final appointment will be set for 2 weeks later and for a reminder to come in fasting. Visit #4 is the at the end of the 4-week intervention period, and data collection will include drawing of blood samples, downloading of actigraphy data with return of the watch and daily sleep diary and completing responses to standard questionnaires. To strengthen the design, we have made time spent with both groups similar throughout the study. All participants will

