receive \$20 after one week of baseline data. At the end of the study, all participants will receive an additional \$30, a certificate of appreciation and a booklet on Healthy Sleep (NHLBI, 2011). Any participants that are noted to have additional risk factors for T2DM will be provided educational material on reducing T2DM risk factors and the suggestion made to follow up with a physician. After serum blood values are analyzed, all participants will be sent a letter with their glucose, insulin and HOMA-IR information along with a description of these values and recommendation for physician follow up. The principal investigator is a registered nurse who will collect the data and administer the sleep intervention. Standard universal precautions will be used during blood draws. Additionally, a GRA, also a registered nurse, will assist with data collection.

**Sample size:** A target sample size of 10 in the SLEEP-Extend group and 10 in the control will be used for this feasibility study (accounting for 20% attrition) given the need for a serum blood test as part of screening a number of participants to meet strict eligibility criteria. Participants will be randomly assigned to either the control or SLEEP-Extend group using a table of random numbers.

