    - i. Intervention Group (SLEEP-Extend intervention): The SLEEP-Extend intervention consists of two components:
      1. One education session (5-10 minutes) consisting of strategies for sleep hygiene which is the routine for going to sleep (an investigator-developed brochure and information based on recommendations from the American Academy of Sleep Medicine and the National Sleep Foundation will be given and reviewed with the subject)
      2. Instructions on extending time in bed by at least one hour but can be up to 2 hours total per night for 4 weeks which can be accomplished by either going to bed earlier or staying in bed later (subject will decide what works best for them).
    - ii. Control group:
      1. One educational session (5-10 minutes) consisting of safety practices used for an urban environment (a safety brochure and safety information developed by the Emory Police department will be given and reviewed with the subject)
  - j. At the end of Visit #2, all subjects will receive \$20.
6. Follow up contact after Visit #2: The subject will be contacted weekly (via text or phone depending on their preference) to reinforce content and answer any questions. Another appointment will be made for Visit #3 (end of the 4 week intervention period) and a reminder to come in fasting as previously described.
7. Visit #3 (End of the 4-week intervention period). The researcher or GRA will meet the subject in a private room located on the university campus.
  - a. The research or GRA (both are registered nurses) will obtain

- i. Fasting serum blood glucose and plasma insulin levels which will be used to calculate HOMA-IR (as previously described).
  - ii. Dietary Screener questionnaire
  - iii. Baecke physical activity questionnaire
  - iv. Meal Timing questionnaire
  - v. Perceived Stress Scale
  - vi. Height and weight as previously described
  - vii. Subject body fat analysis (using a hand-held, non-invasive calibrated scale) (Omron Body Logic Pro, Omron Healthcare, Inc., Vernon Hills, IL)
  - viii. Both groups will be given the Sleep Hygiene Index questionnaire
  - ix. The Control group will also be given the Safety Practices questionnaire.
  - x. Actigraphy data will be downloaded and actigraph and sleep diary will be returned to researcher.
  - xi. Lastly, an exit interview will be conducted to provide the researcher information on areas that can be improved in the study.

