### **Analysis Plan**

Data analysis will include descriptive statistics to characterize the sample and inferential statistics to compare study variables. Sleep characteristics will be expressed as percent change from beginning to end and analyzed with repeat measures ANOVA. Blood levels will also be expressed as percent change from baseline to last draw. Correlational analysis will be used with sleep variables and IR. Regression analysis including components of sleep, BMI, dietary and physical activity will be conducted to examine the association of sleep factors and IR. Responses to the exit interview questions will be content coded and interrater reliability assessed.

- 3. Data and Safety Monitoring and Reporting: If there is an adverse or reportable event, the IRB will be notified promptly via the eIRB reportable event form. Also, the event will be documented in a tracking log. The sponsor does not require reporting above and beyond Emory IRB reporting requirements. This study does not include more than minimal risk; however, the PI will periodically review documentation to ensure accuracy and completeness.

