### **Protection of Human Subjects**

Emory IRB approval will be obtained. Participation in the study will be voluntary and written, informed consent will be obtained. Portable data will be locked in a secured cabinet. Study participant names will be on the contact form and consents, and these will be stored separately from study questionnaires. Only the researchers will have access to each participant's identity and the data. All data will have unique number identifiers and will be stored in password/firewall-protected electronic files. The PI will work closely with the IT department to ensure computer safety. Data access will be limited to a few key personnel involved in the study. All data will be maintained in the locked filing cabinets in the PI's office at Emory University for seven years following completion of the study after which the data will be shredded. Actigraphy is not considered a dangerous procedure; however special precautions will be made to educate the participant on the removal of the actigraphy if any irritation or allergic reaction should appear. Obtaining blood specimens via venipuncture is not considered a dangerous procedure; however, aseptic technique will be used by the PI (RN) to obtain blood sample. Site will be observed for 20 minutes to ensure no bleeding is present. Any abnormal finding during the study (as stated previously) will be reported to the participant and educational materials as well as physician follow-up instructions will be provided if necessary. The blood samples will be stored in a secure laboratory at Emory University and then analyzed by Cardiovascular Specialty Laboratories, Inc (Atlanta, GA) using standard laboratory approaches with calibrated equipment (see letters of support from [name] and [name]). A snack will be offered after drawing blood. Participant consent form will be written at a maximum of 8th grade reading level, and participants may opt out of the study at any time point.

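### Intervention-period sleep data are retrieved only at the final visit, with no stated procedure for early leavers, and the planned sleep analysis excludes anyone without the last week

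*Combined protocol and SAP*

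**What the plan says.** The combined protocol and SAP contains two visit schedules. Their visit numbers differ, but they agree on when intervention-period sleep data are collected.

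- Informed Consent Process and Visit Details, item 7.a.x (Visit #3, end of the four weeks): "Actigraphy data will be downloaded and actigraph and sleep diary will be returned to researcher".
- PROCEDURES, Visit #4 (also the end of the four weeks): "downloading of actigraphy data with return of the watch and daily sleep diary".
- The Abstract likewise places the download after the intervention period.

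The only earlier download is that of the baseline week, before randomisation. Between randomisation and the last visit the plan has either one telephone call at two weeks (PROCEDURES) or weekly text or phone contact (Visit Details, item 6). Both are for reinforcement and questions.

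On losses, the Sample size paragraph describes the two groups of 10 as "accounting for 20% attrition", and Protection of Human Subjects says that "participants may opt out of the study at any time point". No early-termination visit, mail-back of the device or interim download is described.

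On analysis, Outcome Measures averages sleep over each week of the protocol. The Analysis Plan expresses sleep characteristics as a percentage change between the start and the finish, "analyzed with repeat measures ANOVA". It gives no rule for missing data and defines no analysis set.

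**The concern.** Someone who stops in week 2 or 3 has complete weeks of sleep stored on the watch. Blood results and questionnaires from the final visit would never have been collected for that person, but the sleep outcome has already been recorded. The plan writes down no way to obtain it, and the stated analysis could not use it.

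Two results depend on these data: sleep duration (Aim 2 and H1) and adherence, which informs feasibility (Aim 1). The exit interview also takes place only at the final visit, so for early leavers the watch and diary are the main evidence on whether they managed the extra time in bed. The Alternative Strategies section itself allows that the one-hour increase may be hard to achieve at once. If people leave for that reason, a completers-only result would look better than the randomised group's experience, and the Introduction makes this pilot the basis for a larger study.

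**Working it through.** **Inputs from the documents**
- 10 per group, 20 in total, with a 20% attrition allowance (Sample size).
- Four post-randomisation weeks of wear (Visit Details, item 5.h), summarised as weekly means (Outcome Measures).
- 28 days as the adherence denominator (Outcome Measures).

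**The plan's own figure.** Inflation for dropout is n / (1 − d). With 8 completers per group, 8 / (1 − 0.20) = 10, so 10 per group is consistent with 8 completers. The documents never state 8 and give no alpha, power, effect size or SD, so the 10 cannot be derived from stated inputs.

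The statements of N also conflict. The Abstract says "For this pilot study we will recruit 20 young adults, accounting for attrition", whereas Study Methods says "we will recruit individuals to give us a final N=20 (10 in each group". On the second reading, 20 / 0.80 = 25 must be randomised (13 per group, 26 in total, for equal groups).

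**Data affected as written, if the 20% is lost after randomisation**
- 20 randomised: 0.20 × 20 = 4 people, about 2 per group. They account for 4 × 4 = 16 of 20 × 4 = 80 person-weeks, leaving 64 of 80 (80%).
- 25 randomised: 0.20 × 25 = 5 people. They account for 5 × 4 = 20 of 100 person-weeks, leaving 80 of 100 (80%).

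**What retrieval could recover.** A person who stops during week 1, 2, 3 or 4 has completed 0, 1, 2 or 3 weeks. If stops are evenly spread, the mean is (0 + 1 + 2 + 3) / 4 = 1.5 weeks.
- 20 randomised: 4 × 1.5 = 6 person-weeks, giving 70 of 80 (87.5%). The range is 0 (all stop in week 1; 64 of 80) to 4 × 3 = 12 (all stop in week 4; 76 of 80, 95%).
- 25 randomised: 5 × 1.5 = 7.5, giving 87.5 of 100. The range is 80 to 95.

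Someone who wears the watch throughout and misses only the last visit would return all four weeks. That case lies outside the range above.

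**Whether the stated analysis would use recovered weeks.** The plan does not say whether the ANOVA takes all weekly means or only the first and last.
- First and last only: a person without the last week has no end value, so the percentage change is undefined.
- All weekly means: a standard repeated-measures ANOVA needs every week and removes a person with one missing.

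On both readings, a leaver with one to three good weeks is excluded. Retrieval alone therefore does not repair Aim 2.

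**Adherence.** The denominator is fixed at 28 days, so a leaver can be scored from partial records. The numerator still needs daily time-in-bed records, which the plan retrieves only at the final visit.

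**The case against.** The strongest reply is that the plan is silent here and prohibits nothing. Staff may recover a watch from someone who stops, they have weekly contact through which to ask, and they will presumably want the device back. This stands. A reader might infer that early leavers contribute no sleep data and that Aim 2 cannot be scored for them. The documents support only the narrower statement that no retrieval procedure is stated. The analysis problem remains even when the watch comes back.

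The count of 4 is also conditional. The 20% is not dated. Its attachment to the group sizes suggests loss after randomisation, but in PROCEDURES a baseline week lies between enrolment and randomisation, and losses then would cost no intervention-period data. The conflict over N adds a second uncertainty.

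A reader might further infer a definite upward bias of a given size. For illustration only, assume that leavers make up 20% of the SLEEP-Extend arm. If they gained half as much sleep as completers, the completer mean exceeds the arm mean by 1 / (0.8 + 0.2 × 0.5) − 1 = 11%. If they gained nothing, the excess is 1 / 0.8 − 1 = 25%. These figures follow from the assumption alone. They concern one arm, whereas H1 is a comparison with controls who may also leave. The documents say nothing about who leaves or why, both arms carry the same watch and diary burden, and inclusion requires willingness to extend time in bed. The direction is plausible but not shown.

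Finally, it may be said that this is a minor drafting gap in a 20-person pilot. The small size argues against an expensive remedy, and the one proposed adds no visit or staff.

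**Conclusion.** The concern holds in this form: followed as written, the plan yields a completers-only result for sleep duration (Aim 2, H1) and, in practice, for adherence. There are two causes: no stated procedure for retrieving the watch and diary from people who leave, and an analysis that excludes anyone without the last week.

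About 4 of 20 participants and 16 of 80 person-weeks are affected, or about 5 of 25 participants and 20 of 100 person-weeks if 20 is the final number. This assumes that the 20% is lost after randomisation. Retrieval would return about 6 of the 16 person-weeks under evenly spread losses, and between 0 and 12 otherwise. There is a risk of bias, but its size and direction cannot be established from the documents. The change should be made before enrolment, because weeks that are not retrieved cannot be reconstructed later.

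**What to change.** 1. In both visit schedules (PROCEDURES, and Informed Consent Process and Visit Details), state that when a participant stops or misses the final visit, the watch and diary are requested back, with consent, by drop-off or prepaid mailer. They are then downloaded, and every completed week is used.
2. In the Analysis Plan, replace the percent-change repeated-measures ANOVA for sleep duration with a linear mixed model on weekly mean minutes, with the baseline week as covariate and terms for group, week and group × week. Include everyone with at least one post-randomisation week, under the assigned group.
3. Score adherence over the 28 days already fixed in Outcome Measures, using the retrieved records.
4. Reconcile the statements of N in the Abstract, Study Methods and Sample size, and say whether the 20% is expected before or after randomisation.

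The cost is a few prepaid mailers (for about 4 or 5 people), a line in the consent form and revised analysis wording. The mixed model relies on a missing-at-random assumption, which should be stated. People who stop in week 1 still contribute no weekly mean, so their number should be reported by group.

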## **Objectives**

**Aims:** The aims for this pilot study of young adults ages 18-25 years old with IR (based on established cut points), short sleep (< 7 hours/night) and obesity (BMI  $\geq$  30) are to: 1) evaluate the feasibility and acceptability of a tailored intervention to extend sleep duration (SLEEP-Extend), 2) determine changes in sleep duration after SLEEP-Extend intervention, 3) evaluate IR levels before and after SLEEP-Extend, and 4) explore the potential mediators of diet and physical activity between sleep duration and IR. Our hypotheses are: H1: Individuals undergoing SLEEP-Extend will have longer sleep duration and increased knowledge of sleep hygiene post-intervention compared to controls and, H2: A greater proportion of the SLEEP-Extend group will have a decrease in IR compared to the control group.

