### **Outcome Measures:**

**BMI and baseline blood samples will be obtained at the screening visit.** All other measures will be assessed at the baseline visit and at the end of the 4-week intervention period except for the following: 1) Actigraphy watch will be worn continuously, and daily sleep diary completed for the entire study period, 2) The sleep hygiene pre/post-test and safety pre/post-test (control group only) will be given prior to intervention, immediately post intervention and at end of 4-week intervention period (3 time points), 3) Participant characteristics questionnaire only at baseline, and 4) Both groups will receive the exit survey at end of 4 week intervention period. **Insulin Resistance:** A) Glucose and insulin levels will be measured from fasting serum samples. B) Insulin Resistance will be calculated from the measured glucose and insulin levels using standard formulas. Briefly, serum samples will be collected via venipuncture and analyzed at Cardiovascular Specialty Laboratories, Inc (Atlanta, GA) using standard laboratory approaches with calibrated equipment (See letters of cooperation, from [name] and [name]). These two values will be used to calculate the homeostatic model assessment of insulin resistance (HOMA-IR; blood glucose level X insulin level, divided by 22.5). Elevated values indicate IR. A cutoff score of HOMA-IR < 2.1 as normal and HOMA-IR  $\geq$  2.1 as elevated (evidence of IR) will be used as determined in non-diabetics (Esteghamati et al., 2010). **Sleep Duration:** Using wrist actigraphy (Motionlogger, AMI, Ardsley, NY) along with a sleep diary (required to help validate and score actigraphy data; Martin & Hakim, 2011), we will objectively monitor each participant's 24-hour sleep-wake cycle to obtain average sleep duration (total sleep time) for one week (baseline) prior to random assignment to group and will continue monitoring during the 4 week intervention period. All participants wear the device (looks like a watch) on the wrist continuously for a total of 5 weeks (1 week for baseline sleep and 4 weeks of intervention period), except while bathing or swimming. Leproult and colleagues (2015) had success with adults wearing a wrist actigraph continuously for a total of 8 weeks. This device contains a light sensor that stores activity counts in 1-minute epochs and will detect the onset and offset of sleep using concurrent data from sleep diaries (Buysse et al., 2008; Morgenthaler et al., 2007). The Motionlogger was successfully validated against polysomnography on dimensions of sleep patterns: sleep onset latency, wake time after sleep onset, total sleep time (sleep duration), and sleep efficiency percentage (Cole et al., 1992). Data for each sleep component will be averaged over the 7 days for each week of the protocol (e.g. average sleep efficiency percentage, average total sleep duration) for analysis. Actigraphy has been compared to polysomnography to detect sleep and wakefulness and found to have a sensitivity of .965 and accuracy of .863 (Marino et al., 2013). The sleep diary is necessary to record data to help interpret actigraphy data (time in bed, time awake, and anything that occurs during the night such as waking up in the middle of the night). Participants in the SLEEP-Extend group will also use a daily sleep diary to record any sleep hygiene practices they use. Participants in the control group will use the same daily sleep diary as the SLEEP-Extend group with the difference of recording any safety practices used rather than recording sleep hygiene practices used. **Sleep Hygiene Knowledge:** To assess

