
the fidelity of the intervention, we are including a sleep hygiene test that will be given at 3 time points: as a pre-test, and as a post-test immediately after the education and at the end of the 4-week intervention period. The researcher-developed sleep hygiene questionnaire is based on the sleep hygiene recommendations from the NSF and the American Academy of Sleep Medicine (AASM). Participants will identify true or false if an item is recommended to facilitate sleep. Non-sleep hygiene items will be included. In addition, the control group will receive an investigator-developed instrument with the list of safety practices based on safety information they receive. Both instruments will be reviewed for content validity by a content expert and researcher with measurement expertise. **Physical activity and Dietary characteristics:** Physical activity will be measured by activity levels from the actigraphy monitor as well as self-report using the Baecke questionnaire (Baecke, Burema & Frijters, 1982). Dietary habits will be measured by self-report using the 26-item Dietary Screener (National Cancer Institute, 2015). Both the Baecke questionnaire and Dietary Screener have evidence of validity (Philippaerts, Westerterp, & Lefevre 1999; Thompson et al, 2005). Diet and physical activity are also reported to impact IR, and a recent study found that in adolescent girls, poorer diet and lower physical activity were associated with higher levels of IR (Jiménez-Pavón et al, 2013). Measuring this at baseline and after the 4-week intervention period will allow us to assess if dietary and/or physical activity were mediators between sleep duration and IR. **Adherence to the intervention:** The percent of days extending time in bed will be computed from the total number of days TIB was actually extended by one hour over the total intervention days (4 weeks = 28 days). **Exit Interview:** Participants in both groups will be interviewed after the 4-week intervention period. This investigator-developed interview will assess their satisfaction with the intervention, any difficulties implementing the intervention strategies and what they felt was most effective and if they would recommend others to participate in the intervention. The interview questions will be reviewed by a content expert and researcher with measurement expertise. **Participant Characteristics:** Will be assessed at baseline via an investigator-developed questionnaire which will include T2DM risk factors based on the ADA risk assessment tool [male gender, family history of diabetes, high blood pressure, and physical inactivity (ADA, Are you at risk?)]. Additional data will include age, marital status, and factors that may affect sleep and/or glucose/insulin levels such as work hours, health problems, and medications. Calculation of BMI from height (stadiometer) and weight (calibrated scale) using a standard formula will be obtained. These data will describe the sample, and a total T2DM risk factor score will be calculated by summing the number of risk factors. Other data will be evaluated as potential covariates. BMI will be assessed at screening and at the end of the 4 week intervention period in both groups.

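### Acceptability in Aim 1 rests on one exit interview that may be run by the person who delivered the intervention, and the protocol describes its content in three different ways

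*Combined protocol and SAP*

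**What the plan says.** Aim 1 (Objectives) is to evaluate the feasibility and the acceptability of SLEEP-Extend.

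The exit contact appears in three forms:

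- The opening of Outcome Measures calls it a survey: "Both groups will receive the exit survey at end of 4 week intervention period".
- The Exit Interview paragraph of the same section calls it an interview for both groups, developed by the investigator. It is to "assess their satisfaction with the intervention, any difficulties implementing the intervention strategies and what they felt was most effective", and also to ask whether they would recommend taking part to others. A subject expert and a measurement specialist review the questions.
- Informed Consent Process and Visit Details, item 7a(xi) (Visit #3), says that "an exit interview will be conducted to provide the researcher information on areas that can be improved in the study".

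On staffing, Procedures says: "The principal investigator is a registered nurse who will collect the data and administer the sleep intervention". It continues: "Additionally, a GRA, also a registered nurse, will assist with data collection". For both the intervention visit (Visit #2) and the final visit (Visit #3), Visit Details says: "The researcher or GRA will meet the subject in a private room located on the university campus".

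The Analysis Plan has the interview responses coded by content, with agreement between raters checked. Outcome Measures separately defines adherence as the share of the 28 intervention days on which time in bed was actually lengthened by an hour.

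**The concern.** Questions about satisfaction and willingness to recommend are open to courtesy answers, especially when asked face to face by the person who taught the session. If that happens here, acceptability looks better than it is, and the burdens that a pilot should bring to light are reported less often. The plan has no second source for these items that would show the problem.

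The differing descriptions add to this. Asking how the study could be improved is not the same as asking whether the intervention was acceptable. Staff who work from the visit schedule have only the first question in front of them.

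**Working it through.** The plan states no figure for acceptability: no score, threshold or expected rate. There is nothing to reproduce, so the check sets the relevant texts side by side.

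**1. Is the interview the only measure of satisfaction?** Yes. The other instruments in Outcome Measures and Visit Details cover sleep, sleep hygiene, safety practices, diet, meal timing, activity, stress, body size, body fat and blood values. Adherence bears on Aim 1, but it records behaviour. A participant can lengthen time in bed and still find it burdensome.

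**2. Who conducts the interview?** Item 7a(xi) is in the passive and names nobody. It is, however, the eleventh entry in a list that opens by assigning the tasks to the researcher or the GRA, both described as registered nurses. Procedures describes the principal investigator and the GRA as the two registered nurses. The interviewer is therefore one of these two, and no independent interviewer is named.

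**3. Does that person deliver the intervention?** The principal investigator does, by the explicit statement in Procedures. The GRA is given only a data-collection role there, although Visit Details allows either of them to meet the participant at Visit #2. Overlap between deliverer and interviewer is therefore permitted, but not established for every participant.

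**4. Do the planned safeguards address candour?** They do not.

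| Safeguard | What it checks | Would it detect courtesy answers? |
|---|---|---|
| Expert review of questions | Wording and content | No |
| Agreement between coders | Whether coders classify a given answer alike | No |
| Adherence over 28 days | Time in bed | No; different construct |

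**5. Do the descriptions agree?**

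| Place | Name | Content |
|---|---|---|
| Outcome Measures, opening | Survey | Not stated |
| Outcome Measures, Exit Interview | Interview | Satisfaction, difficulties, most effective part, would recommend |
| Visit Details, item 7a(xi) | Interview | Areas of the study to improve |

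The Abstract and the Analysis Plan also say interview, so the word survey stands alone. The second row is current text, and the third does not withdraw it.

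**6. How many answers are involved?** The target is 10 per group. If the stated 20% attrition falls within that number, 10 × (1 − 0.20) = 8 SLEEP-Extend participants reach the interview. If 10 per group is the final number, all 10 do. The protocol can be read either way. This gives the number of respondents, not the size of any bias.

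**The case against.** The strongest reply is that the plan already specifies the right content, has it reviewed by experts, and is run by a team of two who will know both sections. On that view, item 7a(xi) is checklist shorthand and the mismatch is editorial. Much of this stands. A reader might infer from the visit schedule that satisfaction will not be collected. The documents do not support that, because the Outcome Measures paragraph is in force and the Analysis Plan refers to the same interview questions.

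A reader might also infer that the answers will be biased upward. That too goes further than the text. The GRA may conduct the interview, a prompt about improvements invites criticism, and the Outcome Measures content asks directly about difficulties. What remains is a risk, and it falls mainly on the satisfaction and recommendation items.

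Two further inferences fail:

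- The $30 and certificate at the final visit go to all participants at its end, and nothing ties them to the answers. They are not evidence of pressure.
- The Introduction makes the larger study conditional on feasibility, longer sleep and preliminary evidence of improved insulin resistance. It does not name acceptability, so the decision to proceed cannot be said to turn on this interview.

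Finally, an interview allows follow-up questions, which suits a pilot. That is a good reason to keep it, but not to make it the sole source of the satisfaction items.

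**Conclusion.** The point holds as a cheap improvement to how half of Aim 1 is measured. Acceptability depends on one interview, which the person who delivered the intervention may conduct, and nothing in the plan would reveal overly favourable answers. The inconsistent descriptions are a smaller matter of wording, to be settled in the same edit.

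The size cannot be given. The plan reports no acceptability percentage, sets no criterion for it, and offers no rate of courtesy answers. Any shift in percentage points would rest wholly on assumed inputs.

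The conclusion rests on two readings: that the researcher in Visit Details is the principal investigator, as the matching descriptions of two registered nurses indicate, and that the opening of item 7a governs the interview listed under it. If someone outside the delivery of the intervention in fact conducts every interview, the risk is smaller, but the protocol should then say so.

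**What to change.** 1. Use one name for the instrument throughout, and carry the four topics from the Exit Interview paragraph of Outcome Measures into item 7a(xi).
2. Put those topics (satisfaction, difficulties, most effective part, would recommend) on a short self-completed form identified by study number. The participant fills it in alone and seals it before the interview starts.
3. Report acceptability for the SLEEP-Extend group from that form, alongside adherence.
4. Keep the interview for open comments on the study and follow-up on difficulties, with content coding as planned.

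The cost is one page, a wording change and a few more minutes at the last visit, with no extra staff or visit. Ratings will probably be less favourable. The form remains linkable through the study number, because the researchers hold participants' identities, so it reduces the pressure to please but does not remove it.
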